### 9.1 Severity of an Adverse Event

The Investigator, based on his/her clinical judgment and the following definitions, must rate severity of the adverse event:

- Mild; Awareness of signs or symptoms, but easily tolerated; are of minor irritant type; causing no loss of time from normal activities; symptoms would generally not require medication or a medical evaluation; signs or symptoms are transient (e.g., headache treated with acetaminophen, common cold, etc. would be considered mild).
- Moderate; Interferes with the subject's usual activity and/or requires symptomatic treatment.
- Severe; Symptom(s) causing severe discomfort and significant impact of the subject's usual activity and requires treatment.

### 9.2 Relationship of Adverse Event to Device and/or Procedure

The Investigator, based on his/her clinical judgment and the following definitions, must determine the relationship of the adverse event to the device and/or procedure:

- Possible: The AE/SAE follows a reasonable temporal sequence from the time of study procedure, and/or follows a known response pattern to the study procedure but could have been produced by other factors.
- Probable: The AE/SAE follows a reasonable temporal sequence from the time of study procedure, follows a known response pattern to the study procedure, and cannot reasonably have been produced by other factors.
- Definite: The AE/SAE follows a reasonable temporal sequence from the time of study procedure; follows a known response pattern to the study procedure; and cannot have been produced by other factors.

[figure not shown]

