### **3.2 Secondary Objectives:**

- Evaluate IPSS and QoL after discontinuation of indwelling bladder catheter (IBC) post PAE
- Evaluation of device-related adverse events
- Evaluation of procedure-related adverse events
- Evaluate frequency of indwelling bladder catheter (IBC) removal post PAE
- Technical Success
  - Successful embolization of treated prostate gland
- Evaluation of additional treatments for refractory or recurrent LUTS due to BPH post PAE
- Evaluation of change from baseline in erectile function at 12 months post PAE using the Sexual Health Inventory for Men (SHIM). 12-16

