#### **8.1.2 Secondary Endpoints**

The following are the secondary endpoints:

- IPSS measured at 3, 12, and 24 months post-baseline
- Device or Procedure-Related Adverse event rate at post-procedure, 3, 12, and 24 months
- Technical Success defined as the successful embolization of the treated prostate gland
- Frequency of indwelling bladder catheter removal post PAE at 3, 12, and 24 months
- Number of patients and types of treatment for refractory or recurrent LUTS due to BPH post PAE at 3, 12, and 24 months
- Change from baseline in Sexual Health Inventory for Men (SHIM) at 12 months post-PAE.

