### 8.5.4 Safety Analyses

All device or procedure related adverse events (AEs) collected will be summarized cumulatively throughout the follow-up time. The frequency count of AEs and the unique number of subjects who had the AEs will be presented. Also, the frequency and percentage of patients who had a Serious AE (SAE), or a treatment-related serious AE will be tabulated separately. If a patient experienced multiple AEs, only the most severe event or the most intense relationship to the study device would be counted within an AE code. The following information will be reported about each AE; start date, stop date, severity, relationship, expectedness, outcome, and duration.

The time-sensitive nature of any response variable may be displayed by using a Kaplan-Meier plot.

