## 9 Device or Procedure-Related Adverse Events

A Device or Procedure-related adverse event is defined in this post market study as any event that began on or after the date of the PAE procedure and is considered related to the study procedure and/or device by the investigator. All related events must be reported in the case report form and followed until resolution.

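### Device-related and procedure-related adverse events are separate objectives, but the plan specifies only a pooled rate, and section 9.2 defines no grading for the device

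*Combined protocol and SAP*

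**What the plan says.** All references are to the combined protocol and SAP.

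- **Objectives (3.2).** Two separate secondary objectives are listed: "Evaluation of device-related adverse events" and "Evaluation of procedure-related adverse events".
- **Endpoint (8.1.2).** The only adverse event endpoint is "Device or Procedure-Related Adverse event rate at post-procedure, 3, 12, and 24 months".
- **Event definition (9, repeated for serious events in 9.3).** An event qualifies if it "is considered related to the study procedure and/or device by the investigator".
- **Causality (9.2).** The investigator "must determine the relationship of the adverse event to the device and/or procedure". The grades then describe the procedure. Possible applies to an event that "follows a reasonable temporal sequence from the time of study procedure, and/or follows a known response pattern to the study procedure" but could have another cause. Probable requires plausible timing and that the event "follows a known response pattern to the study procedure, and cannot reasonably have been produced by other factors". Definite has the same structure with other causes ruled out.
- **Analysis (8.5.3.2 and 8.5.4).** Section 8.5.3.2 refers to section 9.3 for the rates. Section 8.5.4 summarizes the pooled events cumulatively, lists a relationship for each event, and says that for a patient with several events "only the most severe event or the most intense relationship to the study device would be counted within an AE code".
- **Safety monitor (18).** An independent monitor adjudicates specified events and must at least weigh each against the documented risks of the device, of vascular embolization and of PAE.

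**The concern.** This is a single-arm post-market study of one named embolic device, and its safety results will be read as evidence about that device. A stated objective on device-related events needs three things: a rating that identifies such events, a numerator and denominator, and an analysis. If the only specified rate combines events attributed to the Microspheres with events attributed to the procedure, the report can follow the plan in full and still leave that objective unanswered. Separating the events after the data are in would mean rating causality again in retrospect, with the results already known.

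**Working it through.** The plan states no adverse event rate, so there is no figure to reproduce. The check has two parts: follow the objective through the text, then show what a pooled rate can say about one of its components.

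**1. From objective to analysis**

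| Step | Section | Device identified separately? |
|---|---|---|
| Objective | 3.2 | Yes, as its own objective |
| Event definition | 9, 9.3 | No, procedure and/or device |
| Data collection items | 6.2 to 6.4, Table 1 | No, pooled wording |
| Causality lead-in | 9.2 | Named, but in one and/or determination |
| Possible, Probable, Definite | 9.2 | No, all three refer to the procedure |
| Endpoint | 8.1.2 | No, one pooled rate |
| Section cited for the rates | 8.5.3.2, to 9.3 | No; 9.3 holds a definition and seriousness criteria, with no rate |
| Safety summary | 8.5.4 | No, pooled set |
| Counting rule | 8.5.4 | Yes, but by a device rating that 9.2 does not define |
| Safety monitor | 18 | Yes, as a review duty; no rate is defined |

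The device stands apart at the objective, in the counting rule and in the monitor's review. None of these supplies a numerator, a denominator or a rate, and nothing requires two ratings per event.

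**2. What the pooled rate can tell**

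Let D be the patients with a device-related event and P those with a procedure-related event. The pooled endpoint estimates

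Pr(D or P) = Pr(D) + Pr(P) − Pr(D and P).

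Since D is contained in (D or P), 0 ≤ Pr(D) ≤ Pr(D or P). The pooled rate is an upper bound for the device-related rate and gives no estimate within that range.

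**Illustration.** The event counts are assumptions. N = 500 is the planned maximum in 8.3; the number evaluable at each time point under 8.5.1.5 may be smaller. Intervals are Clopper-Pearson, the method named in 8.5.1.7: lower limit Beta(0.025; x, N − x + 1), upper limit Beta(0.975; x + 1, N − x).

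Assumed pooled count 100/500 = 20.0%, exact 95% CI 16.6% to 23.8%. The same pooled result is compatible with every row below.

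| Assumed share of these patients with a device-related event | Patients | Device-related rate | Exact 95% CI |
|---|---|---|---|
| 0% | 0/500 | 0.0% | 0% to 0.74% |
| 10% | 10/500 | 2.0% | 0.96% to 3.65% |
| 25% | 25/500 | 5.0% | 3.26% to 7.29% |
| 50% | 50/500 | 10.0% | 7.51% to 12.97% |
| 100% | 100/500 | 20.0% | 16.6% to 23.8% |

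With an assumed pooled rate of 10% or 30%, the device-related rate could run from 0% to 10% or from 0% to 30%. The intervals cover sampling error only; misattribution between device and procedure would come on top.

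**The case against.** The strongest reply is that the plan does deal with device attribution. The heading and lead-in of 9.2 name the device. The study procedure is PAE with these Microspheres, so a known response to the procedure can reasonably include a response to the device. Section 8.5.4 lists a relationship for every event and presupposes one to the device. Section 18 has an independent monitor assess events against device risks under a charter that is not in the documents. The eCRF is not available either, and a figure following the 9.2 definitions is not shown; separate fields may already exist. Many embolic events arise from device and procedure together and resist a clean split. Finally, this is a descriptive secondary objective with no safety hypothesis test.

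Much of this stands. It rules out the reading that the plan is silent on device attribution or that device-related counts could not be produced. It does not supply a specified rate, and counts drawn from 8.5.4 would rest on a device grading that the protocol text does not define.

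A reader might also infer three stronger points that the documents do not support:

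- **That a collagen or gelatin reaction is the only Microsphere risk recognized.** It is the only item under the device heading in section 18. The embolization list there also includes passage of Microspheres into unintended arteries, foreign body reactions and allergy to embolic material.
- **That the 8.5.4 rule cannot be applied to procedure-only events.** Its severity alternative applies to any event. The rule is ambiguous, but it can still be used.
- **That access-site and embolization-procedure events drive the pooled rate.** No adverse event rates are given, and section 18 names post-PAE syndrome as the most frequent complication.

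Nor does sharing a causality grade merge different events: 8.5.4 counts within an event code, so a hematoma and an allergic reaction remain distinguishable.

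**Conclusion.** The concern holds for the protocol and SAP text. Two objectives lead to one pooled endpoint, all three causality grades are worded for the procedure, the counting rule uses a device rating that 9.2 does not define, and the cross-reference for the rates leads to a section without any. The plan as written specifies no device-related rate.

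The size is a loss of identification: the device-related rate is known only to lie between zero and the pooled rate. The 0% to 20% range rests on an assumed 100 of 500 men with a related event.

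The primary IPSS endpoint is unaffected. The change should be made because a stated secondary objective otherwise has no analysis. If the eCRF already records separate device and procedure ratings, what remains is to write the definitions and the separate rates into the plan.

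**What to change.** - **9.2.** Require two ratings per event, one for relationship to the Microspheres and one for relationship to the PAE procedure. Word the grade definitions for each, add a grade for no relationship, and allow both ratings to be positive where an event cannot be split.
- **8.1.2 and 8.5.4.** Report three rates with exact 95% confidence intervals: device-related, procedure-related and either. The last keeps the present pooled endpoint.
- **8.5.4.** Apply the counting rule within each relationship, and say whether severity or strength of relationship decides which event is kept.
- **8.5.3.2.** Point the cross-reference to the section that contains the rate analysis.

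The cost is one more eCRF field per event if it does not already exist, two more table columns, protocol and SAP wording, and re-rating of any events already recorded. Sites will have slightly more work. Some events will be rated to both, so the device-related and procedure-related rates will overlap and should not be added together.

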### 9.3 Device or Procedure-Related Serious Adverse Events

A device or procedure-related serious adverse event is defined in this post market study as any event that began on or after the date of the PAE procedure and is considered related to the study procedure and/or device by the investigator. A device or procedure-related adverse event will be considered serious if it meets one of the following criteria:

- Results in death
- Is life-threatening. Life-threatening means that the patient was at immediate risk of death from the reaction as it occurred, i.e., it does not include a reaction which hypothetically might have caused death had it occurred in a more severe form
- Requires in-patient hospitalization or prolongation of existing hospitalization. Hospitalization admissions and/or surgical operations scheduled to occur during the study period, but planned prior to study entry are not considered AEs if the illness or disease existed before the patient was enrolled in the trial, provided that it did not deteriorate in an unexpected manner during the trial (e.g., surgery performed earlier than planned)
- Results in persistent or significant disability/incapacity. Disability is defined as a substantial disruption of a person's ability to conduct normal life functions
- Is a congenital anomaly/birth defect
- Is an important medical event. An important medical event is an event that may not result in death, be life-threatening, or require hospitalization, but may be considered an SAE when, based upon appropriate medical judgment, it may jeopardize the patient or patient and may require medical or surgical intervention to prevent one of the outcomes listed in the definitions

#### 9.4 Reporting of Serious Adverse Events

Any treatment-related SAE that occurs on or after the date of the PAE or worsened in severity or frequency after the PAE must be reported to the Sponsor immediately (not to exceed 24 hours within site notification of the event) in the case report form or via email. It is the responsibility of Investigators to inform their IRB/EC of complications or serious injury as required by their IRB/EC procedure and/or federal law. Merit Medical is responsible for relaying information about serious adverse events and/or treatment related adverse events to the other participating Investigators and regulatory bodies as required.

#### 10 Data Recording and Retention

The sponsor will provide each site with access to an electronic CRF for study data recording. All trial documents must be retained for a minimum of two years after the completion of the post market study or longer per the Sponsor's request.

#### 11 Publication Policy

The Sponsor intends to publish the clinical results of this investigation and the terms are delineated in the Investigator/Site Clinical Trial Agreement. In addition, Sponsor will list this post market study on [clinicaltrials.gov](http://clinicaltrials.gov).

## **12 Good Clinical Practice (GCP)**

The study will be conducted in accordance with the International Conference on Harmonization (ICH) E6 for Good Clinical Practice (GCP). The investigators will be thoroughly familiar with the appropriate use of the treatment procedure as described in the protocol. Essential clinical documents will be maintained to demonstrate the validity of the study and the integrity of the data collected. Master files should be established at the beginning of the study, maintained for the duration of the trial, and retained according to the appropriate regulations.

## **13 Ethical Considerations**

The study will be conducted in accordance with ethical principles founded in the Declaration of Helsinki. The IRB/EC will review all appropriate study documentation to safeguard the rights, safety and well-being of the patients. The protocol, informed consent, advertisements (if applicable), written information given to the patients, safety updates, annual progress reports, and any revisions to these documents will be provided to the IRB/EC by the investigator.

## **14 Patient Informed Consent**

After the study has been fully explained, written informed consent will be obtained from either the patient or his guardian or legal representative prior to any study procedures. The method of obtaining and documenting the informed consent and the contents of the consent will comply with ICH-GCP and all applicable regulatory requirement(s).

Patients who wish to provide information for follow-up visits or receive reminders by email or text must sign a consent for this to be done over unsecured media.

## **15 Subject Enrollment**

All patients requiring an intervention due to reasons detailed in this protocol are potential study candidates and shall be screened for eligibility. Subjects who are consented and meet all the study inclusion criteria and none of the study exclusion criteria and are treated or attempted to be treated will be considered enrolled into the study.

## **16 Patient Confidentiality**

To maintain patient privacy, all CRFs and study reports will identify the patient by the assigned patient number. The Investigator will grant monitor(s) and auditor(s) from Merit Medical or its designee and regulatory authority(ies), including the FDA, access to the patients' original medical records for verification of data gathered on the CRFs and to audit the data collection process. The patients' confidentiality will be maintained and will not be made publicly available to the extent permitted by the applicable laws and regulations.

## 17 Monitoring, Audit and Inspection

A Merit Medical monitor, or designee, shall monitor each center periodically to monitor the progress of the study and review CRFs and original source documents with the study personnel, to verify accuracy of data recording and appropriate consents. Periodically some/all of the facilities used in the trial (e.g., laboratory) may be reviewed or inspected by the IRB/EC and/or regulatory authorities, including the FDA.

## 18 Safety Medical Monitor

An independent safety medical monitor shall be responsible for systemic review and adjudication of specified events (e.g., all treatment-related adverse events and all deaths) . At a minimum, assess the reported event with the associated documented risks of device, vascular embolization, and PAE treatment.

Potential risk for Embosphere Microspheres:

- Immune reaction in patients who are hypersensitive to collagen or gelatin (careful consideration should be given prior to using this product in patients who are suspected to be allergic to injections containing gelatin stabilizers)

Potential risk for vascular embolization:

- Paralysis resulting from untargeted embolization or ischemic injury from adjacent tissue edema
- Undesirable reflux or passage of Embosphere Microspheres into normal arteries adjacent to the targeted lesion or through the lesion into other arteries or arterial beds, such as the internal carotid artery, pulmonary, or coronary circulations
- Pulmonary embolism
- Ischemia at an undesirable location, including ischemic stroke, ischemic infarction (including myocardial infarction), and tissue necrosis
- Capillary bed occlusion and tissue damage
- Vessel or lesion rupture and hemorrhage
- Vasospasm
- Recanalization
- Foreign body reactions necessitating medical intervention
- Infection
- Complications related to catheterization (e.g., hematoma at the site of entry, clot formation at the tip of the catheter and subsequent dislodgment, and nerve and/or circulatory injuries, which may result in leg injury)
- Allergic reaction to medications (e.g., analgesics)
- Allergic reaction o contrast media or embolic material
- Pain and/or rash, possibly delayed form the time of embolization
- Death
- Blindness, hearing loss, loss of smell, and/or paralysis

PAE specific potential complications:

- Non-targeted embolization of the rectum, bladder, scrotum, penis, or other areas
- The most frequent post-procedure complication includes “Post-PAE Syndrome,” which includes nausea, vomiting, fever, pelvic pain, burning sensation, dysuria, and frequent or urgent urination
- Skin burn (radiation exposure) from prolonged fluoroscopy time
- Blood in urine, semen, or stool
- Bladder spasm
- Hematoma at the catheter site
- Urinary tract infection
- Urinary retention
- Constipation

The safety medical monitor will be an independent physician with experience in interventional peripheral endovascular procedures for prostate artery embolization. In order to enhance objectivity and reduce the potential for bias, the safety medical monitor shall be independent of the Sponsor as well as the investigational sites and investigators. The methodology for performing these responsibilities shall be developed and outlined in the safety monitoring charter. Operational provisions shall be established to minimize potential bias.

